3.3 Patient enrolment and randomisation

Investigator(s) should keep a record, the subject screening log, of patients who entered Part 1 screening.

The investigator(s) will:

- 1 Obtain a signed Part 1 ICF from the potential patient before any study specific procedures are performed.
- 2 Assign the potential patient a unique enrolment number, beginning with 'E#'.
- 3 Determine patient eligibility (please see asterisked criteria in sections 3.1 and 3.2)
- 4 Obtain signed main study (Part 2) ICF from the potential patient before any Part 2 screening procedures are performed.
- 5 Determine patient eligibility. See Section 3.
- 6 Upon confirmation of eligibility, randomise the patient using the randomisation system which is available for this trial, answering all questions which are asked by the system including questions relative to the stratification factors.
- 7 The randomisation system will randomly assign treatment (savolitinib or sunitinib) and this information will be made available to the site personnel.

If a patient withdraws from participation in the study, then his/her enrolment/randomisation code cannot be reused.

Patient eligibility will be established before treatment randomisation. Once the eligibility of a patient has been confirmed, the investigator (or nominated assistant) should contact the IVRS/IWRS Centralised Randomisation Centre for allocation of randomised therapy. Patients will be identified to the Centralised Randomisation Centre using patient E-code and date of birth. The actual treatment given to individual patients will be determined by a randomisation scheme that has been loaded into the IVRS/IWRS database. The randomisation scheme will be produced by a computer software program called AZRand (AZ Randomisation system) that incorporates a standard procedure for generating random numbers.

A blocked randomisation will be generated and all centres will use the same list in order to minimise any imbalance in the number of patients assigned to each treatment group. The randomisation scheme will be stratified (See Section 3.5) based on:

- IMDC risk categorisation (favourable, intermediate, poor prognosis)
- Treatment naïve versus previously treated with or without a VEGF-TKI.

Every effort should be made to minimise the time between enrolment and starting treatment.

3.4 Procedures for handling incorrectly enrolled or randomised patients

Subjects who fail to meet the eligibility criteria should not, under any circumstances, be enrolled or receive study medication. There can be no exceptions to this rule. Subjects who are enrolled, but subsequently found not to meet all the eligibility criteria must not be randomised or initiated on treatment, and must be withdrawn from the study.

Where a patient does not meet all the eligibility criteria but is randomised in error, or incorrectly started on treatment, the investigator should inform the AstraZeneca study physician immediately, and a discussion should occur between the AstraZeneca study physician and the investigator regarding whether to continue or discontinue the patient from treatment. The AstraZeneca study physician must ensure all decisions are appropriately documented.

3.5 Methods for assigning treatment groups

Eligible patients will be randomised in a 1:1 ratio. The actual treatment given to individual patients will be determined by a randomisation scheme that has been loaded into the Interactive Voice Response System / Interactive Web Response System (IVRS/IWRS) database.

Patients will be stratified based on the IMDC risk group criteria (Kroeger et al 2013), using the number of predefined risk factors to assign patients into favourable, intermediate, or poor prognostic groups as well as whether they are treatment naïve versus previously treated with or without a VEGF-TKI. The VEGF-TKIs that are currently most used in PRCC treatment include sunitinib, bevacizumab, cabozantinib, pazopanib, axitinib, sorafenib, and lenvatinib (in combination with everolimus).

The IMDC model includes the following 6 independent predictors of poor survival at study entry: Karnofsky performance status <80%, interval from initial diagnosis to first systemic treatment <1 year, haemoglobin <LLN, corrected calcium >ULN, absolute neutrophil count >ULN, and platelet count >ULN. According to the number of poor prognostic factors, patients are segregated into favourable (0 factors), intermediate (1 to 2 factors), and poor

(≥ 3 factors) risk groups. Based on these stratification criteria, patients will be stratified to 1 of the following 9 strata:

- Treatment naïve, favourable prognosis.
- Treatment naïve, intermediate prognosis.
- Treatment naïve, poor prognosis.
- Previous treatment not including a VEGF TKI, favourable prognosis.
- Previous treatment not including a VEGF TKI, intermediate prognosis.
- Previous treatment not including a VEGF TKI, poor prognosis.
- Previous treatment with a VEGF TKI, favourable prognosis.
- Previous treatment with a VEGF TKI, intermediate prognosis.
- Previous treatment with a VEGF TKI, poor prognosis.

Specific information concerning the use of IVRS/IWRS will be provided in a separate manual.

It is recommended that patients commence study treatment on the day of randomisation if possible, and if not, then ideally within 3 days.

3.6 Restrictions

3.6.1 Need for contraception

There are no studies in pregnant women taking savolitinib or sunitinib. However, studies in animals have shown that either drug may cause harm to a foetus. Patients of child bearing potential and their partners who are sexually active, must agree to the use of highly effective forms of contraception while taking study medication. Female patients on savolitinib must continue to use contraception for 1 month after their last dose. Acceptable methods of contraception include full abstinence, tubal ligation, combined oral, transdermal or intra-vaginal hormonal contraceptives, medroxyprogesterone injections (eg, Depo-Provera), copper-banded intra-uterine devices, hormone impregnated intra-uterine systems, and vasectomised partners. All methods of contraception (with the exception of total abstinence) should be used in combination with the use of a condom by their male sexual partner for intercourse.

Studies in animals taking savolitinib have shown some abnormalities in sperm development. Therefore, male patients must use a condom during sexual intercourse with a female partner of childbearing potential (pregnant or not) and refrain from donating sperm during the study and for 6 months after their last dose. For details refer to Appendix D “Acceptable Birth Control Methods”.

3.6.2 Prohibited concomitant medications and treatments

No other investigational therapy should be given to patients. No anticancer agents should be given to patients other than the study medications. If such agents are required for a patient, then the patient must first be withdrawn from the study.

Herbal preparations/medicines

Herbal preparations/medications are not allowed throughout the study. These herbal medications include, but are not limited to St. John's wort, kava, ephedra (ma huang), ginkgo biloba, dehydroepiandrosterone (DHEA), yohimbe, saw palmetto, and ginseng. Patients should stop using these herbal medications 7 days prior to the date of randomisation (3 weeks for St John's wort).

Statins

For patients on savolitinib, discontinuation of statins is advised unless considered essential, in which case, the patients should be prescribed the lowest available dose and monitored for the effects of increased statin exposure.

Acetaminophen (Paracetamol)

The administration of acetaminophen (paracetamol) is restricted to 3 grams per day, or the maximum dose approved locally (if less than 3 grams per day) during the study. In the event of an elevation in hepatic transaminases or bilirubin, the use of acetaminophen should be avoided until resolution of the affected parameter.

Drugs that prolong QT interval

The concomitant administration of drugs known to prolong QT interval is restricted unless considered essential due to patient management, in which case, patients should be closely monitored with more frequent ECGs. Additional guidance on drugs known to prolong QT interval is provided in Appendix I.

Food restrictions

Patients should abstain from eating grapefruit and Seville oranges (and other products containing these fruits, eg, grapefruit juice or marmalade) during the study.

UV exposure

During savolitinib therapy and for 4 weeks after the last dose, patients should be advised to avoid prolonged exposure to the sun, wear protective clothing, a hat and seek shade from the sun as far as possible; in addition, SPF30+ sunscreen should be used. Exposure to other sources of UV light including sunbeds and tanning booths, etc. should be avoided.

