During verification of the institution’s diagnosis of radiographic progression by BICR, participants should continue to receive study treatment if not medically contra-indicated. The decision whether to continue or to withhold study treatment will be at the discretion of the investigator, but if not medically contra-indicated, patients should be strongly encouraged not to start subsequent anti-cancer therapy until BICR-confirmation of PD. If disease progression is not confirmed by BICR, the patient may continue/resume study treatment and must continue to undergo assessments as per Table 1, including tumour evaluations at 6-week intervals (or sooner if felt to be medically indicated) until disease progression is confirmed by

BICR. Those patients who begin subsequent non-study anti-cancer therapy prior to BICR-confirmed PD should continue to undergo tumour assessments, and sites must send each scan to the sponsor-designated vendor until PD is confirmed by BICR.

Regardless of initial treatment, patients will have two options for post-progression therapy following BICR-confirmation of PD:

- 1 Receive subsequent non-study anti-cancer therapy that does not contravene local practice.
- 2 Continue to receive the assigned study treatment as long as in the opinion of the investigator, the patient is deriving benefit and the patient meets the original eligibility criteria in terms of Performance Status and laboratory values. This decision must be discussed with and approved by the AstraZeneca study physician. Such patients will continue to undergo monitoring as per the Study Plan (Table 1).

There will be no cross-over.

An EOT visit will be conducted as soon as possible and preferably within 7 days following the decision to discontinue study medication.

The purpose of this visit is to:

- (a) discuss any further treatment options and/or follow-up.
- (b) discuss the possibility of a biopsy, which should be strongly encouraged, particularly for patients who had responded to treatment (patients may have signed a consent line for this on the Main Study ICF).
- (c) obtain the required EOT tests (Table 1) and collect the ePRO device after the last set of questionnaires are completed.
- (d) collect any unused study medication and study-medication containers from the patient.

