3.7 Post-progression therapy

Regardless of initial treatment, patients will have two options for post-progression therapy following BICR-confirmation of PD:

- 1 Receive subsequent non-study anti-cancer therapy that does not contravene local practice.
- 2 Continue to receive the assigned study treatment as long as in the opinion of the investigator, the patient is deriving benefit, and the patient meets the original eligibility criteria in terms of performance status and laboratory values. This decision must be discussed with and approved by the AstraZeneca study physician. Such patients will continue to undergo monitoring as per the Study Plan (Table 1) while on study treatment.

There will be no cross-over.

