3.8 Discontinuation of investigational product

Patients may be discontinued from savolitinib or sunitinib in the following situations:

- Patient decision. The patient is at any time free to discontinue treatment, without prejudice to further treatment.
- Adverse Event as per study criteria.
- Pregnancy.
- Severe non-compliance with the Clinical Study Protocol.
- BICR-confirmed PD unless the physician feels that the patient is still deriving benefit from the initial treatment and confirms that the patient meets the original eligibility criteria in terms of performance status and laboratory values. This must be discussed with and approved by the AstraZeneca study physician.
- Patients was incorrectly initiated on investigational product (Section 3.4).
- The investigator decides the patient should not be continued on the trial/is no longer deriving benefit from the study medication.

After discontinuation of the study treatment at any point in the study, all ongoing AEs or SAEs must be followed until resolution or until the event becomes stable (or returns to baseline) unless, in the investigator's opinion the condition is unlikely to resolve due to the patients underlying disease, or the patient is lost to follow up (see Section 6.3.2). All new AEs and SAEs occurring during the 30 calendar days after the last dose of study treatment must be reported (if SAEs, they must be reported to AstraZeneca within 24 hours as described in Section 6.4) and followed to resolution or until the event becomes stable (or returns to baseline) or is unlikely to resolve further in the opinion of the investigator. Patients should be contacted or seen 30 days (± 7 days) after discontinuing the last dose of study medication to collect and /or complete AE information. Any untoward event occurring subsequent to the 30-day follow-up AE reporting period that the investigator assesses as possibly related to the study medication should also be reported as an AE.

AstraZeneca retains the right to request additional information for any patient with ongoing AE(s)/SAE(s) at the end of the study, if judged necessary.

Any patient who has not yet shown BICR-confirmed PD at discontinuation of study medication should continue to be followed with centrally reviewed scans until there is BICR-confirmation of PD, regardless of whether subsequent anti-cancer therapy is started.

3.8.1 Procedures for discontinuation of a patient from study treatment prior to BICR-confirmed PD

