Patients who discontinue study-medication prior to BICR-confirmed PD will be asked about the reason(s) for discontinuation and the presence of any AEs. In addition, the date of discontinuation, the reason and any medications taken at the time of discontinuation will be recorded on the eCRF. If a patient discontinues study treatment, the study monitor must be informed immediately.

If the reason for study medication discontinuation is due to investigator-assessment of PD using RECIST 1.1 (but prior to BICR confirmation due to delay or a BICR discrepancy), patients should be encouraged, if not medically contraindicated, to not start subsequent anti-cancer therapy and continue to undergo disease assessments until BICR-confirmed PD. Once there is BICR-confirmed PD, patients will be followed for PFS2 and OS as per Sections 4.3.3 and 4.3.4.

However, if this is not an option for the patient and/or physician, or if the study medication was discontinued for any other reason other than PD, then an EOT visit will be conducted as soon as possible and preferably within 7 days following the decision to discontinue study medication.

The purpose of this visit for patients who discontinue study-drug prior to BICR-confirmed PD is to:

- (a) discuss any additional treatment options and follow-up.
- (b) discuss the possibility of a biopsy, which should be strongly encouraged, particularly for patients who had responded to treatment (patients may have signed a consent line for this on the Main Study ICF).
- (c) obtain the required EOT tests (Table 1) and collect the ePRO device after the last set of questionnaires are completed.
- (d) collect any unused study medication and study-medication containers from the patient.

By discontinuing study treatment, the patient is not withdrawn from the study. If a patient decides to voluntarily withdraw (ie, patient choice), then the Withdrawal ICF (Informed Consent Form Addendum – Options for Withdrawal of Consent) should be used to determine

if they are willing to undergo follow-up. Section 3.9.2 outlines the criteria for withdrawal from study.

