3.9 Criteria for withdrawal from the study

Reasons for withdrawal from the study:

- Voluntary withdrawal by the patient who is at any time free to discontinue their participation in the study without prejudice to further treatment.
- Incorrectly enrolled patients ie, the patient does not meet the required inclusion/exclusion criteria for the study. This option is only applicable to patients not randomised into the study (ie, screen failures identified prior to randomisation).

If a patient voluntarily withdraws consent, they will fill out the Withdrawal ICF (Informed Consent Form Addendum – Options for Withdrawal of Consent) and be specifically asked if they are withdrawing consent for further follow-up, eg, survival calls.

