3.9.2 Withdrawal of the informed consent

Patients are at any time free to withdraw from the study (study medication and assessments), without prejudice to further treatment. Such patients will always be asked about the reason(s) and the presence of any AEs. If possible, they will be seen and assessed by an investigator. Adverse events will be followed up (see Sections 6.3.2 and Section 4.3.2). All study medication and empty study medication bottles should be returned by the patient as well as the electronic PRO (ePRO) devices.

If a patient withdraws from the study, then his/her enrolment/randomisation code cannot be reused.

In the event that the patient has actively withdrawn consent to the processing of their personal data, the vital status of the patient can be obtained by site personnel from publicly available resources where it is possible to do so under applicable local laws.

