4.3.2 Safety follow-up

If there are no ongoing SAE/AEs at the time of study medication discontinuation, the safety follow-up with the patient 30 (± 7) days after discontinuation of study medication can be done through telephone contact, capturing any new SAEs/AEs and concomitant meds including new therapy. The primary purpose is to follow-up any AEs ongoing at the time of discontinuation and to assess any new AEs that may have occurred since discontinuation. Any AE/ SAE/ abnormal laboratory findings that are ongoing at the time of study treatment discontinuation or any new treatment related events within 30 days of the last study treatment must be followed up to resolution or until the event becomes stable (or returns to baseline) or is unlikely to resolve further in the opinion of the investigator.

AstraZeneca retains the right to request additional information for any patient with ongoing AE(s)/SAE(s) at the end of the study, if judged necessary.

4.3.3 Follow-up for second progression on subsequent anti-cancer therapy after PD by RECIST 1.1 (PFS2)

Following discontinuation of study medication for PD by RECIST 1.1 as determined by investigator assessment, patients that started on subsequent therapy post-progression will continue to be followed at least every 12 weeks by investigator assessment for documentation of second progression. Subsequent therapy and OS will also be collected. Determination of PD for PFS2 will be by institutional call only. Patients who choose to continue on study therapy after the investigator confirmed PD will not be considered to have a second PFS-event until they have discontinued study medication and started subsequent anti-cancer therapy.

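### Section 3.6.2 sends patients who need another anticancer agent out of the study, while the PFS and PFS2 sections require them to stay in follow-up

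*Protocol*

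**What the plan says.** Section 3.6.2 of the protocol (prohibited concomitant medications) allows no anticancer agent besides the study medications and then states: "If such agents are required for a patient, then the patient must first be withdrawn from the study".

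Other current sections deal with the same patient differently:

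- **Section 1.4:** "Those patients who begin subsequent non-study anti-cancer therapy prior to BICR-confirmed PD should continue to undergo tumour assessments". Section 5.1.3 repeats this.
- **Section 3.8:** a patient without BICR-confirmed progression when study medication stops "should continue to be followed with centrally reviewed scans until there is BICR-confirmation of PD, regardless of whether subsequent anti-cancer therapy is started".
- **Section 3.7:** one of the two options after BICR-confirmed progression is "Receive subsequent non-study anti-cancer therapy that does not contravene local practice".
- **Section 3.8.1:** "By discontinuing study treatment, the patient is not withdrawn from the study".
- **Section 3.9:** two reasons for leaving the study are listed, voluntary withdrawal and incorrect enrolment. Of the second it says: "This option is only applicable to patients not randomised into the study".
- **Section 3.9.2**, on withdrawal of consent: "Patients are at any time free to withdraw from the study (study medication and assessments), without prejudice to further treatment".
- **Section 4.3.3:** after progression on study medication, "patients that started on subsequent therapy post-progression will continue to be followed at least every 12 weeks by investigator assessment", to document second progression.
- **Section 8.3.1.2:** PFS events count whether or not another anticancer therapy came first.
- **Section 8.3.1.8:** the PFS2 event is a progression after subsequent non-study therapy has begun, or death.

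**The concern.** The protocol distinguishes stopping study treatment from leaving the study, and Section 3.6.2 uses the term for leaving the study. It has no exception and no pointer to Sections 3.7 or 3.8. A site that follows it stops collecting the data that the endpoint sections need.

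What is lost depends on when the patient switches:

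- **Before BICR-confirmed progression.** Scans stop and PFS is censored at the last evaluable assessment. If the switch was made because progression was suspected, the censoring is informative. A death found later through the vital-status search would count for PFS only if it came before two visits had been missed (Section 8.3.1.2). Treatment is open label, so the frequency of such switches could differ by arm, and that would bias the hazard ratio.
- **After BICR-confirmed progression.** The loss falls mainly on PFS2, an exploratory endpoint.
- **Overall survival** is largely protected. Section 4.3.4 requires the status of withdrawn patients to be obtained, and Section 3.9 has withdrawing patients asked specifically about survival calls.

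About 50 patients are expected (Section 8.1), so few events can be spared. Randomised patients stay on the study plan after the close of recruitment (Section 1.4), so the sentence still applies to them.

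**Working it through.** **1. The rules side by side, for a randomised patient who needs another anticancer agent**

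| Question | Section 3.6.2 | Rest of the protocol |
|---|---|---|
| Does the patient leave the study? | Yes, before the agent is given | No. Stopping treatment is not withdrawal (3.8.1), and 3.9 lists no reason that fits |
| Do scans continue before BICR-confirmed progression? | No, if leaving the study ends assessments, as 3.9.2 describes it | Yes (1.4, 3.8, 5.1.3) |
| Does a later progression count for PFS? | It would not be observed | Yes (8.3.1.2) |
| Is PFS2 followed? | No scheduled follow-up remains | Yes, at least every 12 weeks (4.3.3, 8.3.1.8) |

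No single course of action satisfies both columns.

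**2. Size of the possible effect**

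The protocol gives no figure for early switching and no expected BICR event count. The 36 events in Section 9.3 are an investigator-assessed trigger. What follows is therefore illustration only.

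*Equal loss in both arms.* If a fraction q of BICR events is lost, the standard error of ln(HR) is multiplied by 1/√(1 − q), whatever the event count:

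- q = 0.10: 1/√0.90 = 1.054, up 5%
- q = 0.20: 1/√0.80 = 1.118, up 12%
- q = 0.30: 1/√0.70 = 1.195, up 20%

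*Unequal loss, closed form.* If every lost patient is censored just before progression, the observed event hazard in an arm is multiplied by (1 − q), so the apparent HR = true HR × (1 − q for savolitinib)/(1 − q for sunitinib).

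- 25% lost on sunitinib, 10% on savolitinib: 0.60 × 0.90/0.75 = 0.72
- Reversed: 0.60 × 0.75/0.90 = 0.50

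*Simulation.* Inputs from the protocol: true HR 0.60 and sunitinib median PFS of 4 months, exponential (the initial design assumptions in Section 8.1), and scans every 6 weeks. Assumed: 20,000 patients per arm; administrative censoring uniform between 7.5 and 20 months; lost patients censored either at the last scan before detected progression (share f) or at a random exponential time with mean 6 months (share 1 − f). Cox hazard ratios:

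| Loss, sunitinib / savolitinib | f = 1 | f = 0.5 |
|---|---|---|
| 10% / 10% | 0.594 | 0.597 |
| 20% / 20% | 0.594 | 0.603 |
| 30% / 30% | 0.591 | 0.596 |
| 25% / 10% | 0.694 | 0.646 |
| 10% / 25% | 0.516 | 0.545 |

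Repeat runs gave the same pattern, moving individual values by a few hundredths with the random draw and the handling of tied scan dates. Equal loss costs precision. Unequal loss shifts the estimate, and the direction depends on which arm loses more.

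**The case against.** The best defence is that the sentence sits under prohibited concomitant medications, so it concerns agents given alongside study medication and means withdrawal from study treatment. That is probably the intent. The protocol is loose with these terms elsewhere: Section 5.2.5.1 uses both leaving the study and stopping study treatment for a positive pregnancy test. The phrase about medication and assessments in Section 3.9.2 belongs to withdrawal of consent, so it is not a general definition. Section 3.7 alone does not say that patients on subsequent therapy remain in the study; Section 4.3.3 supplies that. The specific sections are numerous and explicit, and nothing shows that any site stopped scans because of Section 3.6.2.

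The early-switch group may also be small. Sites are told to encourage patients to wait for BICR confirmation (Sections 1.4 and 5.1.3), and central review should generally take no more than 10 days. PFS2 is exploratory and only summarised. Taking 36 events for scale, the standard error of ln(HR) is about 2/√36 = 0.33. A shift from 0.60 to 0.69 is ln(0.69/0.60) = 0.14, about 0.4 of a standard error, and its direction is unknown.

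These points limit the likely harm and show what the sponsor meant. They do not change the sentence, which is mandatory, names the study rather than treatment, and makes no exception. Loose terminology elsewhere makes a literal reading by a site more likely, not less.

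**Conclusion.** The contradiction is real and rests on the text alone: Section 3.6.2 cannot be followed together with Sections 1.4, 3.8, 3.8.1, 3.9, 4.3.3, 5.1.3, 8.3.1.2 and 8.3.1.8. The definitions of PFS and PFS2 are not at fault.

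The consequence is conditional on a site applying the sentence literally. If that happened about equally in both arms, the cost would be mainly precision. If it differed by arm to the extent assumed above, a true hazard ratio of 0.60 could appear anywhere from about 0.52 to 0.69. The loss shares, switch times and administrative censoring are assumptions, and the HR of 0.60 belongs to the original 180-patient plan. Confidence is high in the contradiction; the size of any effect is unknown. It should be fixed because it touches collection of the primary endpoint and is easy to correct.

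**What to change.** Reconcile the sentence in Section 3.6.2 with Sections 1.4, 3.7, 3.8, 3.9, 4.3.3, 5.1.3, 8.3.1.2 and 8.3.1.8, so that starting another anticancer agent does not by itself end study follow-up. Add cross-references to Section 3.8 for continued centrally reviewed scans and to Sections 4.3.3 and 4.3.4 for PFS2 and survival follow-up, and send sites a short notice.

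The cost is a one-sentence protocol clarification and the notice. No scan, visit or form is added, because the follow-up is already required. The change concerns data collection only and takes no position on which treatment a patient receives or when study treatment stops.
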